### **5.3 Methionine-restricted diet**

Under the supervision of a registered dietitian (either at the site or from the coordinating site) and the site investigator, subjects will receive an individualized dietary prescription that incorporates a methionine-free amino acid-modified

medical food (Hominex-2, Abbott Nutrition) supplemented with low-methionine foods (**Table 2**). Hominex-2 contains a mixture of L-amino acids but lacks methionine. Subjects will be instructed by the dietitian in the preparation of Hominex-2 shakes to deliver 100% of daily protein requirements (0.8 g/kg/day) and 75% of the caloric requirements. The remaining calories will be met with low-methionine foods, including fruits, vegetables, grains (*e.g.*, specified cereal and bread), margarine and cooking oils. Subjects will be provided with a list of foods that are low in methionine. Calories will not be restricted. Subjects will be encouraged to follow their usual level of physical activity and instructed to maintain a daily diet and exercise diary that will be reviewed by the dietitian. Subjects will take the MR diet days 1 through 5 of each week (defined as a 7-day period) while taking the ONC201. Subjects may resume a general diet on days 6 and 7 each week. Phase I and phase II trials of a methionine-free diet alone or in combination with chemotherapy in subjects with metastatic or recurrent solid tumors have confirmed the safety and tolerability of methionine deprivation (up to 39 weeks)[24, 25].

A 24-hour dietary recall exercise [40] will be completed by a dietitian prior to starting the methionine restricted diet during cycle 1. The recall and food diaries will be analyzed using Food Processor® Nutrition and Fitness Software, ESHA Research, Salem, OR, USA. Food intake will be entered in and a report detailing the nutritional components of the food taken will be generated and provided back to the dietitian. Gender, age, height and weight will be entered for use with the analysis of the diet taken. This dietary analysis will not be provided to the subjects.

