**Table 3: Dose adjustment rules for Adverse Events (in addition to Table 5 below)**

CTCAE Grade	Management for the methionine-restricted diet
Weight loss	
Grade 2 or higher	Methionine restricted diet must be discontinued.
Homocysteine levels (to be captured as: Metabolism and Nutrition disorders – other, specify)	
Grade 2 or higher	Methionine restricted diet must be discontinued

Normal homocysteine levels are 5-15 micro mol/L.

For purposes of this study homocysteine levels will be graded per the table below:

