## 7. STUDY CALENDARS AND EVALUATIONS

Cycle = 21 days	Screening	Cycle 1	Cycle 2	Odd # cycles Begin at Cycle 3	Even # cycles Begin at Cycle 4	End of Treatment	Long-term Follow-up
	-28 days	Day 1 +/- 2 days	Day 1 +/- 2 days	Day 1 +/- 2 days	Day 1 +/- 2 days	35 days from last dose of study treatment +/- 5 days	Every 3 months (+/- 7 days) for 2 years from EOT
Informed consent	X						
Medical history	X						
Diagnosis and staging	X						
Physical Exam	X	X 	X	X	X	X	
Vital signs, wt, waist circumference  , ECOG performance status	X	X 	X	X	X	X	
AEs & concomitant medications, drug diary review 	X	X	X	X	X	X	
LABORATORY ASSESSMENTS							
CBC with differential (minimum to include: Hgb, WBC, Plt, ANC)	X	X 	X	X	X	X	
CMP 	X	X 	X	X	X	X	
Blood for metabolic indices 		X	X		X	X	
Homocysteine/cysteine 		X		X		X	

Cycle = 21 days	Screening	Cycle 1	Cycle 2	Odd # cycles Begin at Cycle 3	Even # cycles Begin at Cycle 4	End of Treatment	Long-term Follow-up
	-28 days	Day 1 +/- 2 days	Day 1 +/- 2 days	Day 1 +/- 2 days	Day 1 +/- 2 days	35 days from last dose of study treatment +/- 5 days	Every 3 months (+/- 7 days) for 2 years from EOT
Pregnancy test (serum) 	- 7 days	X 					
Diet/Exercise Diary		X	X	X	X		
24 Hour Dietary Recall Form		X					
DISEASE ASSESSMENTS							
CT chest, CT or MRI of abdomen and pelvis 	X				X 		X
MRI brain	X 						
Bone scan	X 				X 		
TREATMENT EXPOSURE							
ONC201		Days 3 and 4, weekly	Days 3 and 4, weekly	Days 3 and 4, weekly	Days 3 and 4, weekly		
MR diet		Days 1 - 5 weekly	Days 1 - 5 weekly	Days 1 - 5 weekly	Days 1 - 5 weekly		
CORRELATIVE STUDIES (SPECIMEN COLLECTION)							
Archival Tissue 	X						
Circulating tumor cells		X 	X 			X 	
Plasma methionine & methionine metabolites		X 	X 		X 	X 	
FOLLOW-UP							
Survival							X

- (1) Blood will be taken to assess metabolic indices at baseline, cycle 2 day 5, then day 5 of every other cycle, and at end of treatment. Indices are fasting: glucose, insulin, IGF-1, and leptin levels. If necessary, these labs may be drawn as early as day 2, but prefer to be as close to day 5 as possible without going over.

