- (2) Blood will be taken to assess plasma methionine levels at baseline, cycle 2 day 5, then day 5 of every other cycle, and at end of treatment. Subjects must be fasting. If necessary, these labs may be drawn as early as day 2, but prefer to be as close to day 5 as possible without going over.
- (3) If clinically indicated.
- (4) Optional biopsy prior to study entry.
- (5) Blood for circulating tumor cells will be taken at baseline, day 5 of cycle 2, and at end of treatment. If necessary, these labs may be drawn as early as day 2, but prefer to be as close to day 5 as possible without going over.
- (6) For women of childbearing potential. To be completed within 7 days of randomization. Must be repeated at cycle 1 day 1 if not completed in previous 7 days.
- (7) Subjects whose treatment is interrupted or permanently discontinued due to an adverse event (including lab values) should be followed per section 11.1.1.
- (8) Waist circumference, optional if not possible due to site limitations. Not required at screening.
- (9) CMP to include sodium, potassium, chloride, carbon dioxide, glucose, BUN, creatinine, calcium, albumin, total protein, alkaline phosphatase, aspartate aminotransferase (AST), alanine aminotransferase (ALT), and total bilirubin.
- (10) CT chest with or without contrast and CT with contrast or MRI of Abdomen/Pelvis to be completed during screening and  $\leq$  7 days prior to every third cycle starting at cycle four (approximately every 9 weeks; e.g. cycles 4, 7, 10, etc.). If subjects discontinue study treatment prior to disease progression, scans during follow-up will be completed per standard of care, but RECIST measurements must be completed until disease progression or start of new anti-cancer therapy.
- (11) Homocysteine/cysteine level at: baseline and every 3 cycles while on study (C1, C4, C7, etc.) and at end of treatment.
- (12) One block or 10 unstained slides.
- (13) labs/physical exam/ECOG PS does not need to be repeated if done within 7 days prior to C1D1

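### The homocysteine diet-stop rule has two conflicting sampling schedules, and after the Cycle 1 Day 1 baseline neither gives a routine clinical reading in the first six weeks

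*Combined protocol and SAP*

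**What the plan says.** Section 6.1 gives two triggers for ending the diet: weight loss and raised homocysteine. For homocysteine of grade 2 or higher, Table 3 states "Methionine restricted diet must be discontinued". The grades are the trial's own ("For purposes of this study homocysteine levels will be graded per the table below"), and Table 4 starts grade 2 at 30 micromol/L.

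The section 7 calendar sets the measurements:

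- **Homocysteine row.** Marked at Cycle 1, in the column "Odd # cycles Begin at Cycle 3", and at End of Treatment. Screening, Cycle 2 and the even-cycle column are blank.
- **Footnote 11, attached to that row.** "Homocysteine/cysteine level at: baseline and every 3 cycles while on study (C1, C4, C7, etc.) and at end of treatment".
- **Weight.** The row beginning "Vital signs, wt, waist circumference" is marked at every cycle.
- **Pre-treatment window.** Footnote 13 says "labs/physical exam/ECOG PS does not need to be repeated if done within 7 days prior to C1D1". The Cycle 1 marks for CBC and CMP carry it; the homocysteine mark does not.
- **Existing Day 5 blood.** Footnote 1 schedules fasting "metabolic indices at baseline, cycle 2 day 5, then day 5 of every other cycle", and footnote 2 does the same for plasma methionine. Both allow a draw from Day 2.

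Section 8.3 lists homocysteine among the metabolites assayed in that research plasma, which is kept at -80 C and shipped in batches. Under section 5.3 the diet runs on days 1 to 5 of each week, beginning on Cycle 1 Day 1. No eligibility criterion in section 3 uses homocysteine.

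**The concern.** A mandatory stopping threshold protects subjects only if someone measures the quantity in time to act. Here a site cannot follow both the row and the footnote. Cycles 3 and 5 appear only in the row, Cycle 4 only in the footnote, and Cycle 7 in both. Under either schedule, Cycle 2 has no clinical value, although the other Table 3 trigger, weight, is checked then.

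The baseline sample is drawn on the day the diet begins, within the calendar's window of two days either side, and nothing requires the result to be reviewed first.

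Under footnote 11 some subjects could have no on-treatment clinical value at all. The first restaging scan falls within 7 days before Cycle 4 (footnote 10), and progression ends protocol therapy (6.3). A subject who progresses at that scan is next tested at End of Treatment, 35 days after the last dose. The safety of adding the diet is a secondary objective (2.2.4), so data the trial set out to collect are affected too.

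**Working it through.** **Inputs.** Cycle of 21 days (5.2); diet on days 1 to 5 of each week, with one day a week allowed to be skipped (5.3, Table 2); visit window of 2 days either side (section 7); ONC201 on days 3 and 4 of each week (5.2).

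**Formula.** Study day = (cycle - 1) x 21 + day.

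**Check against the plan's own figure.** Footnote 10 describes Cycles 4, 7 and 10 as about 9 weeks apart. C4D1 = 3 x 21 + 1 = 64 and C7D1 = 6 x 21 + 1 = 127. The gaps are 64 - 1 = 63 and 127 - 64 = 63 days, and 63 / 7 = 9.0 weeks. This agrees.

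**First on-treatment reading.** Diet days completed before the sample:

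| Sample | Study day (window) | Diet days at 5 a week | With one day a week skipped |
|---|---|---|---|
| C2D1, weight only | 22 | 3 x 5 = 15 | 3 x 4 = 12 |
| C2D5, research draw | 26 (24-28) | 15 + 4 = 19 | 15 or 16 |
| C3D1, row | 43 (41-45) | 6 x 5 = 30 | 6 x 4 = 24 |
| C4D1, footnote 11 | 64 (62-66) | 9 x 5 = 45 | 9 x 4 = 36 |

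A local assay at C2D5 brings the first on-treatment sample forward by 64 - 26 = 38 days against footnote 11, or 43 - 26 = 17 days against the row. If the blood is taken on C2D2, as the footnotes allow, the nominal day is 23.

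**Gaps between clinical readings, in days.**

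- Footnote 11 alone: 63, 63.
- Row alone: 42, 42, 42.
- Footnote 11 plus C2D5: 25, 38, 63.
- Row plus C2D5: 25, 17, 42, 42.

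The added assay closes the early gap only. The later gaps depend on which schedule is kept.

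**Effect on evaluability.** Sections 13.3 and 13.6 refer to 80% of ONC201 plus diet over the first two cycles. Two cycles hold 6 x 5 = 30 diet days, and 80% of 30 is 24. A stop at C2D5 leaves 19 or 20 diet days, depending on whether that day counts: 19 / 30 = 63% and 20 / 30 = 67%. On that wording the subject falls short and is replaced. Section 6.4 and the parenthesis in 13.3 count only ONC201, with at least 9 doses needed. By C2D5 a subject has had 4 x 2 = 8 doses, and 6.1 lets ONC201 continue after the diet ends, so the ninth can follow in the next week. A stop prompted by a day 43 or day 64 sample comes after all 30 diet days and raises no such question.

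**The case against.** **The row-footnote mismatch may be editorial.** Calendar columns are coarse and footnotes supply detail. Imaging is marked on treatment only under even cycles, while its footnote includes Cycle 7. Footnote 11 names its cycles and matches the imaging rhythm, so it may be the intended schedule. That is plausible, but it leaves sites with two instructions, and if the footnote governs, the first on-treatment reading is the later one.

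**No benefit from earlier timing is demonstrated.** The documents give no trigger rate, and several statements point to low risk. Hominex-2 is used in homocystinuria (10.2), methionine-free cells showed modest falls in some metabolites (8.3), and earlier methionine-free diets are described as safe for up to 39 weeks (5.3). This stands and limits the weight of the point. It does not explain why a mandatory trigger is checked later than the other one.

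**The earlier assay has a cost.** As shown above, it creates the one time point at which a diet stop could remove a subject from the efficacy set on the 13.3 and 13.6 wording. This stands. A reader might infer from 6.4 alone that evaluability is untouched; 13.3 and 13.6 do not allow that conclusion.

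**Tempting stronger readings.**

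- A reader might infer that the rule cannot act at all in the first six weeks. It can: the Cycle 1 Day 1 sample is in both schedules, and Table 3 does not exempt it.
- A reader might infer that Day 1 is the wrong day, because "Subjects may resume a general diet on days 6 and 7 each week" and each Day 1 sample on treatment follows that break. The documents do not show whether Day 5 values are higher or lower.
- A reader might infer that a baseline of 30 or more already bars the diet. Table 3 governs discontinuation for adverse events, so barring entry would be a new rule.

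**Conclusion.** The point holds as a minor-to-moderate safety and consistency issue. The diet-stop rule at 30 micromol/L has two schedules that cannot both be followed. Apart from a baseline value that need not be seen before the diet starts, neither gives a routine clinical reading in the first six weeks: the first is nominal day 43 after 30 scheduled diet days, or day 64 after 45. The homocysteine in the C2 Day 5 research plasma does not fill the gap.

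This rests on the calendar marks being read correctly from the table, on 21-day cycles without delay, and on routine testing only. Unscheduled tests are not forbidden, but none is required. Day 26 is a nominal sampling day; assay turnaround is not given, so the result comes later. No claim is made about how often the threshold would be crossed or about harm from a later reading.

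**What to change.** 1. **One schedule.** Make the row and footnote 11 agree. The row (Day 1 of Cycles 3, 5, 7 and so on) is preferable because it gives the earlier reading and the shorter 42-day gap. Through C7D1 it means 3 on-treatment assays instead of 2.
2. **One early reading.** Add a locally reported homocysteine at the existing fasting C2 Day 5 draw, with 30 micromol/L or more triggering Table 3. No new visit is needed. The cost is one assay per subject, up to 34 for the planned sample, and possibly an extra tube, since the research tube is heparinised and may not suit a local assay.
3. **Baseline before diet.** Draw it within 7 days before C1D1, alongside the CBC and CMP, and review it before the first diet day. If 30 or more is to bar starting the diet, write that rule into section 3 or 6.1 and say whether such a subject may take ONC201 alone and be counted for response.
4. **Evaluability.** State in 13.3 and 13.6, consistently with 6.4, that a diet stop required by Table 3 does not by itself remove a subject from the efficacy set.

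The remaining downside is possibly a few earlier diet stops.

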## 8. BIOSPECIMEN STUDIES AND PROCEDURES

### 8.1 Tumor tissue

Subjects will be consented for use of archived tissue for analysis. To determine the effects of dietary MR on tumor expression of TRAIL receptors, mRNA levels of TRAIL-R1 and TRAIL-R2 will be determined by real-time PCR. In addition, quantitative immunofluorescence of cell surface TRAIL-R1 and TRAIL-R2 expression in breast tumor cells identified by cytokeratin expression will be determined by automated quantitative analysis (AQUA) of digitally captured images. These studies will be performed in the UW Carbone Cancer Center Translational Research Initiatives in

Pathology (TRIP) Lab under the supervision of our co-investigator [name]. We will also determine the effects of treatment on the expression of the cancer stem cell markers CD44 and CD24 by immunohistochemistry.

### **8.2 Circulating tumor cells (CTCs)**

If funding is secured, CTCs will be enumerated and evaluated for TRAIL expression. We hypothesize that treatment with MR diet will increase the expression of TRAIL receptors on CTCs and reduce the number of CTCs.

**Time points:** CTCs will be collected at baseline, on day 5 of cycle 2, and at end of treatment. If the CTC sample is not collected at baseline, the remaining samples should not be collected. Missed CTC samples will not be considered a protocol deviation.

Please note that CTC samples must be shipped Monday –Thursdays only. Samples must be shipped to arrive at the [name] lab by Fridays by 12:00 p.m. CTC samples will be drawn only at those sites identified by the coordinating site as having adequate resources (shipping and funding) to provide the samples.

#### **Sample Requirements:**

Please refer to the Study Procedures Manual for sample collection, processing, labeling, and shipping instructions.

### **8.3 Plasma methionine and methionine metabolites**

Blood will be collected after an overnight fast before dietary methionine restriction at baseline, cycle 2 day 5, then day 5 of every other cycle, and at end of treatment. Plasma will be stored at -80° C for analyses of methionine and its metabolites. Plasma concentrations of methionine and methionine metabolites [5'-methylthioadenosine (MTA), homocysteine (Hcy), S-adenosylhomocysteine (SAH), and S-adenosylmethionine (SAM)] will be determined by high-throughput targeted LC-MS assay to measure methionine and these metabolites. Using these methods, we demonstrated that TNBC cells grown in 0% methionine have robust reductions in methionine levels and modest reductions in some methionine metabolites. Plasma methionine levels are predicted to serve as an index of dietary compliance.

Blood samples (one 6 mL heparinized green top tube per timepoint) will be drawn and processed at the CRU, stored in [name] lab at -80° C, and sent in batches to the Laboratory of [name] in the UW Department of Chemistry. All samples provided will be identified by UWCCC study number, unique subject number and date and time sample was collected. Outside sites should refer to the Study Procedures Manual for collection, processing, labeling, and shipping instructions.

### **8.4 Confidentiality of biospecimens**

Samples that are collected will be identified by the study number, the subject's study number assigned at the time of registration to the trial and the date and time of

sample collection. Any material issued to collaborating researchers will be anonymized and only identified by the subject's unique sequence number, study number, date of collection.

## **9. CRITERIA FOR DISEASE EVALUATION**

The following sections describe the recommended method to track disease response for solid tumor trials as per the Response Evaluation Criteria in Solid Tumors (RECIST) 1.1.[41]

### **9.1 Measurable Disease**

Measurable disease is defined as the presence of at least one measurable lesion. Measurable lesions are defined as those that can be accurately measured in at least one dimension (longest diameter to be recorded) as  $\geq 20$  mm by chest x-ray, as  $\geq 10$  mm with CT scan, or  $\geq 10$  mm with calipers by clinical exam. All tumor measurements must be recorded in millimeters (or decimal fractions of centimeters).

**Malignant Lymph Nodes:** To be considered pathologically enlarged and measurable, a lymph node must be  $\geq 15$  mm in short axis when assessed by CT scan (CT scan slice thickness recommended to be no greater than 5 mm). At baseline and in follow-up, only the short axis will be measured and followed.

### **9.2 Non-measurable Lesions**

All other lesions (or sites of disease), including small lesions (longest diameter  $<10$  mm or pathological lymph nodes with  $\geq 10$  to  $<15$  mm short axis), are considered non-measurable disease. Bone lesions, leptomeningeal disease, ascites, pleural/pericardial effusions, lymphangitis cutis/pulmonitis, inflammatory breast disease, and abdominal masses (not followed by CT or MRI), are considered as non-measurable.

**NOTE:** Cystic lesions that meet the criteria for radiographically defined simple cysts should not be considered as malignant lesions (neither measurable nor non-measurable) since they are, by definition, simple cysts. 'Cystic lesions' thought to represent cystic metastases can be considered as measurable lesions, if they meet the definition of measurability described above. However, if non-cystic lesions are present in the same subject, these are preferred for selection as target lesions.

### **9.3 Target Lesions**

All measurable lesions up to a maximum of 2 lesions per organ and 5 lesions in total, representative of all involved organs, should be identified as target lesions and recorded and measured at baseline. Target lesions should be selected on the basis of their size (lesions with the longest diameter), be representative of all involved organs, but in addition should be those that lend themselves to reproducible repeated measurements. It may be the case that, on occasion, the largest lesion does not lend itself to reproducible measurement in which circumstance the next largest lesion which can be measured reproducibly should be selected. A sum of the

diameters (longest for non-nodal lesions, short axis for nodal lesions) for all target lesions will be calculated and reported as the baseline sum diameters. If lymph nodes are to be included in the sum, then only the short axis is added into the sum. The baseline sum diameters will be used as reference to further characterize any objective tumor regression in the measurable dimension of the disease.

#### **9.4 Non-target Lesions**

All other lesions (or sites of disease) including any measurable lesions over and above the 5 target lesions should be identified as non-target lesions and should also be recorded at baseline. Measurements of these lesions are not required, but the presence, absence, or in rare cases unequivocal progression of each should be noted throughout follow-up.

#### **9.5 Evaluation of Target Lesions**

**NOTE:** In addition to the information below, also see section 4.3.2 in the international criteria proposed by the Response Evaluation Criteria in Solid Tumors (RECIST) Committee, version 1.1 (Eur J Cancer 45;2009:228-247) for special notes on the assessment of target lesions.

Complete Response (CR)	Disappearance of all target lesions. Any pathological lymph nodes (whether target or non-target) must have reduction in short axis to <10 mm.
Partial Response (PR)	At least a 30% decrease in the sum of the diameters of target lesions, taking as reference the baseline sum diameters
Progressive Disease (PD)	At least a 20% increase in the sum of the diameters of target lesions, taking as reference the smallest sum on study (this includes the baseline sum if that is the smallest on study). In addition to the relative increase of 20%, the sum must also demonstrate an absolute increase of at least 5 mm. (Note: the appearance of one or more new lesions is also considered progressions).
Stable Disease (SD)	Neither sufficient shrinkage to qualify for PR nor sufficient increase to qualify for PD, taking as reference the smallest sum diameters while on study

#### **9.6 Evaluation of Non-target Lesions**

Complete Response (CR)	Disappearance of all non-target lesions and normalization of tumor marker level. All lymph nodes must be non-pathological in size (<10 mm short axis)  Note: If tumor markers are initially above the upper normal limit, they must normalize for a
------------------------	---

	subject to be considered in complete clinical response.
Non-CR/ Non-PD	Persistence of one or more non-target lesion(s) and/or maintenance of tumor marker level above the normal limits
Progressive Disease (PD)	Appearance of one or more new lesions and/or unequivocal progression of existing non-target lesions. Unequivocal progression should not normally trump target lesion status. It must be representative of overall disease status change, not a single lesion increase.

Although a clear progression of “non-target” lesions only is exceptional, the opinion of the investigator at the respective participating site should prevail in such circumstances, and the progression status should be confirmed at a later time by the UW investigator.

